### **Methods**

The sequence was generated by a computer, and the patients who met the criteria were allocated in a 1:1 ratio to receive either oral N-acetylcysteine (600 mg, twice daily) or control (receive as-needed therapy) for 12 months. All the participants were followed for up to 12 months. Outpatient and/or telephone visits were obtained for the primary and secondary outcomes at 1, 3, 6, 9, and 12 months. Moreover, compliance and adverse reactions were also documented. The treatment strategy based on current guidelines was instituted for patients with exacerbations. Meanwhile, patients in the N-acetylcysteine group were also required to receive oral N-acetylcysteine (600 mg, twice daily) during the study period. For the control group, interventions would be discontinued once the patient recovered from the exacerbation. Maintenance therapies that had already started in patients with pulmonary ventilation dysfunction prior to enrollment, such as short-acting bronchodilators, long-acting bronchodilators, inhaled glucocorticoids, or theophylline, were continued during the study. However, the use of other mucolytics or expectorants, antioxidant agents, or vitamins with antioxidant properties was not recommended.

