### **Study end-points**

The primary end-point was the incidence of exacerbations in a year, defined as the number of all exacerbations associated with bronchiectasis within one year. An exacerbation of bronchiectasis is defined by the British Thoracic Society guidelines for bronchiectasis. Details regarding symptoms of an exacerbation such as dyspnea, sputum volume (collected over 24 h), sputum properties, fever, and persistent upper respiratory tract infection were also documented by site investigators from all centers.

Secondary end-points included the time to the first exacerbation, 24-h sputum volume, lung function, inflammation indices, quality of life (assessed by COPD assessment test score, CAT score), and adverse events. The volume of 24-h sputum

was measured by a graduated cylinder marked in milliliters. Eligible sputum samples were used for testing sputum microbiological culture and antibiotic resistance. Pulmonary function was assessed three times before recruitment, and the maximum value was used for analysis. Following treatment, pulmonary function was reassessed for forced vital capacity (FVC), FEV1, percentage of predicted FEV1, FEV1/FVC ratio (FEV1/FVC), and inspiratory capacity, etc. Inflammatory markers including serum C-reactive protein (CRP) and the erythrocyte sedimentation rate (ESR) were tested at each visit. The severity of bronchiectasis was quantified by high-resolution computed tomography (HRCT), and the number of lobes involved was counted according to the modified Reiff grade. Furthermore, the degree of dyspnea was assessed by the modified Medical Research Council (mMRC) scale.

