Effect of N-acetylcysteine on Exacerbations of Bronchiectasis (BENE): a randomized controlled trial

Official Title: Effect of N-acetylcysteine on Exacerbations of Bronchiectasis (BENE): a randomized controlled trial

Trial registration: *ClinicalTrials.gov* (NCT02088216) (Registered date: March 5, 2014)

Document Date: November 2, 2018

Statistical analyses

Patients who received at least one assessment visit after randomization were left in the original group for analysis of the results. Continuous data were expressed as the mean \pm standard deviation and were compared using the Student's *t* test. Categorical variables were expressed as a number (%) and were compared using the χ^2 test. Number of exacerbations was described by the median (interquartile range, IQR). The Mann-Whitney U test was performed to compare the difference in the number of exacerbations between the two groups. The primary study end point was the incidence of exacerbations, which is a count and follows Poisson distribution. Negative binomial regression not including other covariates was employed to compute the risk ratio and 95% confidence intervals (CIs) for N-acetylcysteine vs. the control. The time to the first exacerbation was described by Kaplan-Meier curves, and the log-rank test was used to explore the differences in time to the first exacerbation between the two groups. All analyses were conducted with the Statistical Package for the Social Sciences (SPSS) software (version 20.0). A *p* value < 0.05 was considered statistically significant.

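### The primary exacerbation count is analysed with no stated allowance for follow-up time, although patients with partial follow-up are included

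*SAP*

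**What the plan says.** The Protocol (Study end-points) defines the primary end-point as "the number of all exacerbations associated with bronchiectasis within one year". Under Methods it says "All the participants were followed for up to 12 months", with visits at months 1, 3, 6, 9 and 12. Study design assumes 3 exacerbations a year, a 33% reduction, a two-sided 0.05 level and 20% attrition, and arrives at 154 patients.

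The SAP (Statistical analyses) sets the analysis population: "Patients who received at least one assessment visit after randomization were left in the original group for analysis of the results". Completing 12 months is not required.

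Two between-arm analyses of the count follow. After the sentence on the median and IQR comes "The Mann-Whitney U test was performed to compare the difference in the number of exacerbations between the two groups". After a sentence beginning "The primary study end point was the incidence of exacerbations" comes "Negative binomial regression not including other covariates was employed to compute the risk ratio and 95% confidence intervals (CIs) for N-acetylcysteine vs. the control". One rule, that a p "value < 0.05 was considered statistically significant", covers every analysis.

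Neither document mentions an offset, exposure time, a person-time rate or a rule for counts from incomplete follow-up. Neither labels one of the two analyses as primary.

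**The concern.** A raw count over one year is comparable between patients only if each is observed for the year. At 3 exacerbations a year, a patient last seen at month 1 has an expected count of 3 × 1/12 = 0.25. The rank test reads that low count as a good outcome, and a negative binomial model without an offset treats it as a full year's count. If one arm loses more patients, or loses them earlier, its shorter follow-up looks like fewer exacerbations.

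A smaller matter goes with this. The role of Mann-Whitney is left implicit, and the two analyses have different power and sometimes disagree on significance.

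**Working it through.** **1. The plan's own figure.** The documents give no dispersion, SD or formula, so 154 can be neither confirmed nor called wrong. The Poisson log rate ratio formula with the stated inputs gives, per arm, (1.96 + 0.84)² × (1/3 + 1/2.01) / (ln 0.67)² ≈ 41. That is 82 in total, or 103 after dividing by 0.8. A negative binomial dispersion k of about 0.21–0.23 would give 154 with the same inflation, but no such value is stated. The figure is used here only to set 154/2 = 77 per arm.

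**2. Bias without an offset.** Assume that leavers depart uniformly over months 1–12, so on average at 6.5 months. With dropout fraction d, mean follow-up in years is 1 − d × (1 − 6.5/12).

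- d = 0.10 gives 0.9542; d = 0.30 gives 0.8625; d = 0.15 gives 0.9313; d = 0.25 gives 0.8854.
- No true effect, 10% control / 30% N-acetylcysteine: ratio 0.8625/0.9542 = 0.904.
- No true effect, 15% / 25%: 0.8854/0.9313 = 0.951.
- True ratio 0.67, 30% control / 10% N-acetylcysteine: 0.67 × 0.9542/0.8625 = 0.741.
- Equal dropout: mean follow-up cancels and the ratio is essentially unbiased.

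**3. Simulation.** 10,000 trials per scenario in the two tables, with 77 randomized per arm and a control rate of 3 a year. Counts are gamma-Poisson, or Poisson-lognormal with the same mean and variance. The negative binomial (NB) model is fitted by maximum likelihood with estimated dispersion and a Wald test, with and without log follow-up as offset. Mann-Whitney (MW) is tie-corrected. The dispersion, the dropout split and timing, and dropout unrelated to risk are assumptions that the documents do not supply. Monte Carlo standard error is about 0.2 points at 5% and 0.4–0.5 points at 60–86%.

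**4. Power, 3 versus 2.01 a year, 20% dropout in each arm (%).**

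| Counts | k | NB, offset | NB, no offset | MW |
|---|---|---|---|---|
| Gamma-Poisson | 0.2 | 85.9 | 82.6 | 76.4 |
| Gamma-Poisson | 0.5 | 71.1 | 68.8 | 58.5 |
| Poisson-lognormal | 0.2 | 87.1 | 83.5 | 78.6 |
| Poisson-lognormal | 0.5 | 74.0 | 70.8 | 64.2 |
| Gamma-Poisson, half of leavers lost before month 1 and excluded | 0.2 | 83.4 | 81.4 | 76.0 |
| Same | 0.5 | 68.3 | 66.7 | 56.7 |

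Omitting the offset costs between 68.3 − 66.7 = 1.6 and 87.1 − 83.5 = 3.6 points. Mann-Whitney falls short of the negative binomial model by between 83.5 − 78.6 = 4.9 and 71.1 − 58.5 = 12.6 points. With gamma-Poisson counts and all leavers kept, it differs on significance from the offset model in 12.7% (k = 0.2) and 18.0% (k = 0.5) of trials, and from the model without an offset in 9.0% and 15.0%.

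**5. Two-sided error with no effect (%, k = 0.2 / k = 0.5).**

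| Dropout, control / N-acetylcysteine | NB, offset | NB, no offset | MW |
|---|---|---|---|
| 20 / 20 | 5.4 / 5.7 | 5.5 / 5.6 | 5.2 / 5.4 |
| 15 / 25 | 5.4 / 5.3 | 7.2 / 6.4 | 7.5 / 6.6 |
| 10 / 30 | 5.4 / 5.2 | 12.9 / 10.2 | 14.0 / 11.2 |
| 10 / 30, half of leavers lost before month 1 and excluded | 5.5 / 5.1 | 7.6 / 6.5 | 7.5 / 6.8 |

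**6. Reverse split, 30% control / 10% N-acetylcysteine, true ratio 0.67.** In shorter runs, the model without an offset estimates about 0.74–0.75. Its power is about 41–58%, against about 70–86% with the offset.

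**The case against.** **The primary analysis is already implied.** The negative binomial sentence follows the one naming the primary end-point, and the trial is powered on a reduction in yearly incidence, which a rank test does not estimate. This stands: what is missing is a label. A reader might infer two rival primary analyses, with success claimed on either; with equal dropout that rule would have an error of 7.4% (k = 0.2) or 8.0% (k = 0.5) for the offset model or Mann-Whitney. The SAP neither states nor excludes such a rule, so the point does not rest on it. The implied reading is still not airtight, because the SAP's wording gives the group comparison to Mann-Whitney and the estimate to the model.

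**An offset may have been used.** This also stands. The remark that no other covariates enter might be read as ruling an offset out, but it neither states nor excludes one. The offset is unstated, not rejected.

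**Inflated error needs unequal dropout.** This is the strongest objection, and it stands. A reader might infer a false-positive finding in favour of N-acetylcysteine. The documents give no dropout by arm, so they support neither its presence nor its direction. The 20% is a planning allowance that does not say whether leavers contribute partial counts. Telephone visits may keep follow-up going after clinic attendance stops. The month-1 patient is an extreme: the average leaver under the assumed pattern has 6.5 months. An as-needed control with no placebo described makes unequal dropout plausible, but does not show it.

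**Conclusion.** The concern holds as a gap in specification. The stated analyses of the primary count make no declared allowance for follow-up time, although the analysis set admits patients with about one month of it.

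With equal 20% dropout the consequence is modest: error near 5%, an essentially unbiased ratio and about 2–4 points of power lost. Mann-Whitney has about 5–13 points less power than the negative binomial model and differs from it on significance in about 9–18% of trials, depending on whether an offset is used and how counts arise.

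With unequal dropout, analyses without an offset favour the arm that loses more. At 10/30 with no effect, the ratio is about 0.90 and the error about 10–14%, against about 5–6% with the offset. At 15/25 the figures are about 0.95 and 6–7.5%. With the split reversed, a real benefit is understated.

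All sizes rest on assumed dispersion of 0.2–0.5, dropout timing and split, and dropout unrelated to risk. That the offset is not stated is certain from the text. That it changed the trial's result is not shown.

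**What to change.** In the SAP, specify the negative binomial model with log follow-up time as offset and estimated dispersion, and rest the primary conclusion on its rate ratio, 95% CI and p value. Define follow-up time, for example from randomization to the last visit at which exacerbations were recorded, capped at 12 months, and report it by arm. Keep the median and IQR as description and label Mann-Whitney supportive. That label only makes explicit the reading that the Protocol's Study design and the order of the SAP already favour.

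The SAP is dated November 2, 2018, later than the end of screening (December 31, 2016) plus up to 12 months of follow-up. The change should therefore be described as not shown to be prespecified, and both analyses should be reported.

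The cost is a few sentences and one model run. Follow-up time must be taken from the visit records, since the documents do not say that it was stored as a variable. The rank test could no longer establish efficacy on its own. The offset does not correct dropout that is related to exacerbation risk.

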### *Study design*

The Effect of N-acetylcysteine on Exacerbations of Bronchiectasis (BENE) study was a prospective, randomized, controlled, multicenter clinical trial. The main study objective was to assess whether the long-term use of oral N-acetylcysteine (600 mg, twice daily, 12 months) might reduce the incidence of exacerbations and improve the quality of life in patients with bronchiectasis. According to previous clinical data on exacerbations of bronchiectasis and the inclusion criteria that a subpopulation of bronchiectasis patients with at least two exacerbations in the past year were included in our study, we hypothesized that the baseline frequency of exacerbations was 3. Due

to the lack of clinical data on the efficiency of N-acetylcysteine in the treatment of bronchiectasis, we assumed that approximately 154 patients would need to be enrolled in this study to have 80% power to detect a reduction of at least 33% in the yearly exacerbation incidence, assuming a two-sided  $\alpha$  level of 0.05 and 20% attrition.

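### Does the SAP's silence on the negative binomial dispersion leave the primary result open to reversal?

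*SAP*

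**What the plan says.** Under Statistical analyses, the SAP describes the end point: "The primary study end point was the incidence of exacerbations, which is a count and follows Poisson distribution". It then names the model: "Negative binomial regression not including other covariates was employed to compute the risk ratio and 95% confidence intervals". It also compares the number of exacerbations between the groups with a Mann-Whitney U test. It names SPSS 20.0 as the software, with no procedure or option, and does not say how the dispersion is handled or whether standard errors are model-based or robust.

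Under Study end-points, the Protocol gives the primary end point as a yearly count, "defined as the number of all exacerbations associated with bronchiectasis within one year". Under Study design it sets the planning values: "we hypothesized that the baseline frequency of exacerbations was 3", a target of "a reduction of at least 33% in the yearly exacerbation incidence", and "approximately 154 patients would need to be enrolled in this study to have 80% power", with two-sided alpha 0.05 and 20% attrition. It gives no dispersion, standard deviation or formula.

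**The concern.** A Poisson count has k = 0, whereas negative binomial regression is chosen to allow k above 0. Taken literally, the two adjacent SAP sentences disagree. With two groups, no covariates and no stated offset, the fitted risk ratio is the ratio of the two sample means whatever k is. Under model-based standard errors, k therefore acts entirely on the confidence interval and its p value. A value that is too small makes the interval too narrow and raises the false-positive rate; a value that is too large can hide the effect the trial was sized to find. This model supplies the only planned effect estimate and interval for the primary end point, so a reader might fear that the conclusion turns on an undocumented setting. The sample size does not settle the matter, because its stated inputs alone do not lead to 154.

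**Working it through.** **Inputs.** Control rate 3, reduction 33% (so 2.01, ratio 0.67), two-sided alpha 0.05, 80% power, 20% attrition and 154 enrolled (77 per arm) come from the Protocol, Study design. 1:1 allocation comes from Methods. 154 less 20% is 123.2, about 62 per arm. One full year per patient and every k value are assumptions.

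**Sample size first.** The formula for n per arm is (1.96 + 0.8416)² × (1/m + 1/(0.67m) + 2k) / (ln 0.67)².

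- m = 3, k = 0: 40.66, so 41. 41/0.8 = 51.25, so 52 per arm, 104 in total. Using a ratio of exactly 2/3 gives 40 and 40/0.8 = 50 per arm, 100 in total.
- m = 3, k = 0.2: 60.24, so 61. 61/0.8 = 76.25, so 77 per arm, 154 in total.
- t test, difference 1, SD 2: 64 per arm, and 128 × 1.2 = 153.6, also about 154.

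The stated inputs under Poisson do not give 154. A modest, unstated variance input does, and it need not be a dispersion: the t-test route involves no k at all.

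**Effect of k on the interval.** With model-based standard errors, SE(log ratio) = √((1/3 + 1/2.01 + 2k)/n), CI = 0.67 × exp(±1.96 SE), and z = 0.4005/SE.

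| n per arm | k | SE | 95% CI | p |
|---|---|---|---|---|
| 62 | 0 | 0.1158 | 0.53 to 0.84 | 0.0005 |
| 62 | 0.2 | 0.1409 | 0.51 to 0.88 | 0.004 |
| 62 | 0.5 | 0.1718 | 0.48 to 0.94 | 0.02 |
| 62 | 1 | 0.2137 | 0.44 to 1.02 | 0.06 |
| 77 | 0.2 | 0.1264 | 0.52 to 0.86 | 0.0015 |
| 77 | 1 | 0.1917 | 0.46 to 0.98 | 0.037 |

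At 62 per arm, p reaches 0.05 when 2k = (0.4005/1.96)² × 62 − 0.8308 = 1.758, so at k of about 0.88. With k = 1 and 68 per arm, SE = √(2.8308/68) = 0.2040, z = 1.963 and p = 0.0497.

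**Robust standard errors.** In this two-group model each patient's score for the log mean is (y − m)/(1 + km), and the information per arm is nm/(1 + km). The factor (1 + km) cancels in the sandwich variance, leaving Σ(y − m)²/(nm)². In one simulated dataset fitted with k fixed at about 0, 0.2, 1 and 2, the robust SE was 0.1442 every time, while the model-based SE ran from 0.113 to 0.278.

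**Performance with k estimated.** Simulation used 4000 trials per setting, 62 per arm, control rate 3, maximum-likelihood k and a Wald test. At true k = 0.2, power is 82% and false positives are 5.5%. At true k = 0, these are 93% and 4.2%. At true k = 0.5, false positives are 5.4%.

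**Mann-Whitney test.** It uses ranks, so no dispersion setting enters. Simulated power at rates 3 and 2.01 is about 93% at k = 0 and 76% at k = 0.2 (2000 trials).

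**The case for a change.** The strongest case for a change is that the SAP does not exclude a wrong setting. It names a package but no option, and it calls the count Poisson. The consequences would not be trivial: with a Poisson standard error, simulated false positives are 11.7% at true k = 0.2 and 21.8% at true k = 0.5. With k fixed at 1 and true k = 0.2, power falls to 45%, and the verdict on significance differs from the estimated-k fit in 37% of trials. One sentence would remove the doubt.

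The omissions stand, and so does the arithmetic. The inference that the primary conclusion is undetermined does not.

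- A Poisson standard error does not fit the named model. The Poisson remark is loose wording about counts, and choosing negative binomial regression in the next sentence overrides it.
- A fixed k of 1 has no basis in the documents. If the true k is near 1, the estimated and fixed fits agree anyway (median p about 0.05 for both).
- The crossing of 0.05 needs about 62 per arm. The SAP keeps everyone with a post-randomisation visit, and the Protocol places the first visit at month 1. Later dropouts therefore stay in the analysis, though with shorter follow-up.
- The SAP does not say which test is primary. It assigns the between-group comparison of counts to the Mann-Whitney test and gives the regression the task of supplying the ratio and interval.

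**Conclusion.** No change to the plan is needed. Negative binomial regression named without qualification is ordinarily fitted with the dispersion estimated from the data, and on that reading the analysis holds its error rate (4.2% to 5.5% for true k from 0 to 0.5). It also reaches the planned power at k = 0.2, a value compatible with 154. The contrast between p = 0.0005 and p = 0.06 sets a model the SAP does not name against a value of k it does not contain. At k = 0.2 the contrast between the right k and an assumed k = 1 is intervals of 0.51 to 0.88 and 0.44 to 1.02. That applies only with model-based standard errors, a fixed k and fewer than 68 analysed per arm. Nothing in the documents shows that k was fixed.

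The unstated variance input behind 154 is a gap in reporting. It does not show that the trial is too small, and 154 and 80% stand as the planning figures. Giving the fitted dispersion beside the risk ratio would be good practice when results are reported, but it leaves the planned analysis as it is. These conclusions assume one year of follow-up per patient, the target means of 3 and 2.01, and the k values shown, none of which the documents supply.
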